#### 6.5.4.4 Management of Hyperglycemia

When hyperglycemia is suspected, if deemed appropriate by the investigator and in accordance with local T2DM guidelines, additional venous fasting plasma glucose measurements may be performed. In addition, home glucose and urine ketone monitoring to be performed by participants as directed by the investigator based on local clinical practice.

In participants who have sustained hyperglycemia, the following options are preferred:

- An increase in insulin (if used)
- Open-label changes to antidiabetic therapy such as uptitration of sulfonylurea/glitinide dose (if these agents were dose adjusted at the beginning of the study)

Additional drugs listed under the permitted therapies in Table 11 may also be used at the discretion of the investigator or the participant's general practitioner. Any changes should be documented in the relevant section of the eCRF.

#### 6.6 Dose Modification

It is strongly recommended that the investigator make every effort to work with the participant to uptitrate to the target dose.

If a participant is unable to successfully uptitrate to  $200 \mu g$  or needs to reduce the dose below  $200 \mu g$ , they should discontinue treatment with study intervention. The lowest target dose of IP allowed for a participant to continue in the study is  $200 \mu g$ .

Once the participant uptitrates to the  $200~\mu g$  dose, in the event the participant experiences significant tolerability issues during the uptitration or maintenance phase, the investigator may allow the participant to remain at the current dose level for up to 14 days if a dose uptitration step is imminent, before resuming the uptitration regimen, without it constituting a deviation from the protocol.

Once the participant uptitrates to the  $300~\mu g$  dose, in the event the participant experiences significant tolerability issues during the uptitration or maintenance phase, the investigator may reduce the dose level to the previous titration step for 14 days or remain at the current dose level for up to 14 days if a dose uptitration step is imminent, before resuming the uptitration regimen, without it constituting a deviation from the protocol.

The investigator may contact the sponsor for assistance with questions related to titration and tolerability. For management of conditions other than nausea and vomiting, dose reductions of cotadutide may be considered following discussion with the sponsor. Any sponsor agreed dose modification will not constitute a protocol deviation.

# 6.7 Missed Dose

If a participant forgets to inject a study intervention dose, the dose can be administered as soon as the participant remembers. However, if it is more than 12 hours since the participant should have administered the dose, the participant should skip the missed dose and take the next dose as usual on the following day. Please note that when taking the next dose after a missed dose, participant should not take a double dose to make up for the missed dose.

If a participant has missed several consecutive doses of study intervention, there might be a

risk for increased nausea when the participant restarts treatment. Therefore, the investigator should consult with the sponsor for guidance on restarting treatment.

Any interruption of the IP for 7 consecutive days during the uptitration phase or for 14 days during the treatment period (after reaching the target dose of 300 or 600  $\mu$ g) will constitute an important protocol deviation.

#### 6.8 Treatment of Overdose

For this study, any dose of cotadutide greater than 600 µg within a calendar day will be considered an overdose.

In the event of an overdose, the investigator should:

- Evaluate the participant to determine, in consultation with the sponsor, if possible, whether study intervention should be interrupted or whether the dose should be reduced.
- Closely monitor the participant for any AE/SAE and laboratory abnormalities as medically appropriate. Refer to Section 8.3.12.5 for details of AE/SAE reporting related to overdose.

# 6.9 Intervention After the End of the Study

There is no intervention following the end of the study.

# 7 DISCONTINUATION OF STUDY INTERVENTION AND PARTICIPANT DISCONTINUATION/WITHDRAWAL

# 7.1 Discontinuation of Study Intervention

It may be necessary for a participant to permanently discontinue (definitive discontinuation) study intervention. Participants who discontinue study intervention early will have an early discontinuation visit as described in the SoA (Section 1.3). After the early discontinuation visit, participants will be encouraged to remain in the study for all remaining visits and study procedures as outlined in the SoA, with the exception of the urine pregnancy test, dispensation of study intervention and Instructions for Use, and PK sampling. Participants will be encouraged to have the biopsy at Week 48 as planned in the SoA. Participants who are unwilling or unable to wait until Week 48 will have the biopsy procedure as part of the early discontinuation visit if they have received study intervention for at least 36 weeks. Samples for clinical safety laboratory assessments, amylase and lipase, coagulation parameters, and calcitonin do not need to be collected at visits occurring more than 30 days after discontinuation of study intervention except as needed for lab abnormalities/AEs that require follow-up to resolution.

Note that discontinuation from study intervention is NOT the same thing as a withdrawal from the study.

An individual participant will not receive any further IP if any of the following occur:

- Withdrawal of consent/assent from further treatment with IP.
- Lost to follow-up.
- Noncompliance that, in the opinion of the investigator or sponsor, warrants withdrawal (eg, refusal to adhere to scheduled visits).
- Pregnancy in a female participant.
- An AE that, in the opinion of the investigator or the sponsor, contraindicates further dosing; specific examples include:
  - Clinically significant tachyarrhythmias, including but not limited to life-threatening arrhythmia, eg, sustained ventricular tachycardia or ventricular fibrillation.
  - Acute pancreatitis
    - Participants will be instructed to contact the investigator or other healthcare provider if they experience persistent severe abdominal pain, with or without vomiting, because this is the hallmark symptom of acute pancreatitis warranting prompt evaluation of serum amylase and lipase and prompt abdominal ultrasound. If pancreatitis is suspected, study medication should be discontinued. If pancreatitis is confirmed, appropriate treatment should be initiated, and the participant should be carefully monitored until recovery.
  - Suspected or confirmed diagnosis of DILI
    - o In case a participant shows an AST or ALT  $\geq$  3 × ULN together with TBL  $\geq$  2 × ULN, refer to Appendix E. Figure 2 and Figure 3 provide additional guidance in evaluating for DILI in this study population.

Refer to the SoA (Section 1.3) for data to be collected at the time of intervention discontinuation and 4-week follow-up.

# 7.2 Participant Withdrawal from the Study

- A participant may withdraw from the study at any time at his/her own request or may be withdrawn at any time at the discretion of the investigator for safety, behavioral, compliance, or administrative reasons (after discussion with the sponsor). This is expected to be uncommon.
- A participant who considers withdrawing from the study must be informed by the investigator about modified follow-up options (eg, telephone contact, a contact with a relative or treating physician, or information from medical records).

- Refer to SoA for data to be collected at the time of study withdrawal and 4-week followup and for any further evaluations that need to be completed.
- If the participant withdraws consent for disclosure of future information, the sponsor may retain and continue to use any data collected before such a withdrawal of consent.
- If a participant withdraws from the study, it should be confirmed if he/she still agrees for existing samples to be used in line with the original consent. If he/she requests withdrawal of consent for use of samples, destruction of any samples taken and not tested should be carried out in line with what was stated in the informed consent and local regulation. The investigator must document the decision on use of existing samples in the site study records and inform the Global Study Team.

# 7.3 Lost to Follow Up

A participant will be considered lost to follow-up if he/she repeatedly fails to return for scheduled visits and is unable to be contacted by the study site.

The following actions must be taken if a participant fails to return to the clinic for a required study visit:

- The site must attempt to contact the participant and reschedule the missed visit as soon as possible and counsel the participant on the importance of maintaining the assigned visit schedule and ascertain whether the participant wishes to and/or should continue in the study.
- Before a participant is deemed lost to follow up, the investigator or designee must make every effort to regain contact with the participant (where possible, 3 telephone calls and, if necessary, a certified letter to the participant's last known mailing address or local equivalent methods). These contact attempts should be documented in the participant's medical record.
- Should the participant continue to be unreachable, he/she will be considered to be lost to follow up.

Discontinuation of specific sites or of the study as a whole are handled as part of Appendix A.

#### 8 STUDY ASSESSMENTS AND PROCEDURES

Study procedures and their timing are summarized in the SoA (Section 1.3). Protocol waivers or exemptions are not allowed.

Immediate safety concerns should be discussed with the sponsor immediately upon occurrence or awareness to determine if the participant should continue or discontinue study intervention.

Adherence to the study design requirements, including those specified in the SoA, is essential and required for study conduct.

The COVID-19 pandemic and associated guidelines, recommendations, national laws, and local restrictions are constantly evolving. Thus, where possible, other measures for carrying out protocol-related activities, such as but not limited to home nursing, may be required to ensure participant safety.

All screening evaluations must be completed and reviewed to confirm that potential participants meet all eligibility criteria. The investigator will maintain a screening log to record details of all participants screened and to confirm eligibility or record reasons for screening failure, as applicable.

# 8.1 Efficacy Assessments

# 8.1.1 Liver Biopsy-based Histopathology

Liver biopsy samples taken at baseline (either historical [collected within 180 days of randomization] or taken during the screening period), at Week 48, or at Early Discontinuation will be assessed centrally by a Central Pathology Review Committee to determine the NAS and fibrosis staging. Details of liver biopsy procedure are described in the Histopathology Manual.

# 8.1.2 Artificial Intelligence-based Histopathology

Artificial intelligence-based histopathology assessments will be conducted for all histology endpoints related to NAS and fibrosis staging (Bosch et al 2021, Taylor-Weiner et al 2021) at the time points specified in Section 1.3.

#### 8.1.3 FibroScan and FibroScan-derived Biomarkers

FibroScan® will be used to assess liver stiffness and CAP at sites where it is feasible to do so, at the time points specified in Section 1.3. If a site has access to appropriate FibroScan equipment, as well as compatible software and probes, they must complete the assessments per the schedule. If not and the assessment cannot be conducted, this will not constitute a deviation from the protocol. The LSM must be performed in a fasting state and according to site standard procedures. At sites with FibroScan equipment with CAP option available, measurements of liver steatosis must be performed at the specified visits. FibroScan-derived biomarkers will be assessed. FAST score (a combination of FibroScan-derived CAP, LSM, and AST level) and Agile 3+ score (a combination of FibroScan-derived LSM, AST, ALT, platelet, age, sex, and diabetes status) will be calculated for participants at sites that have the required software or access to the website.

# 8.1.4 Height and Weight

Standing height and body weight will be measured at the time points specified in the SoA (Section 1.3).

Height will be measured once at screening only and recorded in centimeters.

The participant's weight should be measured after the participant has removed bulky clothing including shoes. The participant's body weight will be recorded in kilograms to 1 decimal place. Whenever possible, the same scale should be used throughout the study and calibrated on a regular basis as recommended by the manufacturer.

# 8.1.5 Exploratory Biomarker Assessments

Table 12 presents protocol-defined exploratory biomarker assessments. These assessments will be made in accordance with the Laboratory Manual and Section 1.3.

Table 12 Exploratory Biomarker Assessments

Assessment	Biomarker
Hepatic inflammation	ALT and AST (Section 8.2.5)
Disease-specific	Collagen turnover: Pro-C3
biomarkers	ELF TM (components): PIIINP, hyaluronic acid, and TIMP-1
	FIB-4 index (components): platelet count, ALT, AST
	APRI (components): AST, platelet count
	NFS (components): ALT, AST, platelet count, albumin
	BARD score (components): ALT, AST
	FAST score a (components): CAP, LSM, AST (Section 8.1.3)
	Agile 3+ a (components): LSM, AST, ALT, platelet count, age, sex, diabetes status (Section 8.1.3)
Glucose control	HbA1c, fasting plasma glucose, adiponectin, C-peptide
Blood pressure	SBP (Section 8.2.3)
Lipids	Total cholesterol, LDL cholesterol, HDL cholesterol, triglycerides, non-HDL cholesterol
Optional biomarkers (serum based)	Biomarker research, including markers disease status and response to cotadutide (Section 8.5.2)

FAST score and Agile 3+ will be calculated only at sites that have the required software. ALT, alanine aminotransferase; APRI, AST-to-platelet ratio index; AST, aspartate aminotransferase; BARD, body mass index, AST/ALT ratio, diabetes; CAP, controlled attenuation parameter; ELF, enhanced liver fibrosis score; FAST, FibroScan-AST; FIB-4, fibrosis-4; HbA1c, hemoglobin A1c; HDL, high-density lipoprotein; LDL, low-density lipoprotein; LSM, liver stiffness measurement; NFS, non-alcoholic fatty liver disease fibrosis score; PIIINP, amino-terminal propeptide of type III-procollagen, Pro-C3, released N-terminal propeptide of type III collagen; SBP, systolic blood pressure; TIMP-1, tissue inhibitor of metalloproteinase type-1

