Urine for albumin and creatinine	X			X			X			X	X	
HbA1c (Section 8.1.5)	X			X			X			X	X	
Fasting serum lipid panel (Section 8.1.5)	X									X	X	
Pre-dose blood for PK analysis (Section 8.4)	X	X		X			X			X	X	X
Serum for immunogenicity (ADA) (Section 8.4.2)	X	X		X			X			X	X	X
Blood sampling for ELF (Section 8.1.5)	X									X	X	

Table 4 Schedule of Activities for Part A: Treatment Period and Follow-up

				ŗ	Freatmen	nent Period						
Week	0	4	8	12	16	20	24	32	40	48		Follow-up
Visit	V2	V3	V4	V5	V6	V7	V8	V9	V10	V11 (EOT)	Visit b 4 weeks after EO	4 weeks after EOT or E/D (± 5d) a
Day	1	29	57	85	113	141	169	225	281	337		
(visit window $\pm x$ days) a	1	± 5d	± 5d	± 5d	± 5d	± 5d	± 5d	± 5d	± 5d	± 5d		
Blood sampling for Pro-C3 (Section 8.1.5)	X									X	X	
FIB-4 computed score (Section 8.1.5)	X									X	X	
Blood for fasting plasma glucose-(Section 8.1.5)	X									X	X	
Blood for C-peptide (Section 8.1.5)	X									X	X	
Blood for adiponectin (Section 8.1.5)	X									X	X	
Genomics Initiative optional, exploratory genetic sample (Section 8.6, Appendix D) °	X											
Optional biomarker serum sample (for biomarker research) (Section 8.5.2)	X									X	X	

Participants should withhold alcohol and refrain from intense exercise for 24 hours prior to each study site visit.

- Visit windows should be calculated from Day 1. Visit 2 (randomization) may be scheduled any day following confirmation that participant meets all eligibility criteria including eligibility reading from the central pathology review of the biopsy (historical or on-study) sample and laboratory report assessments from the central laboratory (eg, the screening period does not need to be a full 8 weeks). Follow-up visit conducted 4 weeks (± 5 d) after EOT visit or E/D visit. For participants who discontinue study intervention permanently and do not continue with study visits, follow-up visit should be performed 4 weeks (± 5 d) after the E/D visit. For participants who discontinue study intervention early but continue with study visits, follow-up visit should be performed 4 weeks (± 5 d) after the EOT.
- b Performed in event of early discontinuation of study intervention or withdrawal from study.
- c Activities related to demonstration and training on SC administration can be conducted at Visit 1 and/or prior to randomization at Visit 2.

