#### 9.4.1 General Considerations

The primary analyses will be of safety. No formal hypothesis testing will be performed. Treatments will be compared in tables using descriptive statistics.

Exploratory efficacy analyses will use nominal 2-sided 5% significance levels (equivalent to nominal 1-sided 2.5% significance levels) unless otherwise stated.

The primary estimand of interest for the histological endpoints will use the treatment policy strategy. The treatment policy approach applies to intercurrent events of treatment discontinuation, deviations from the protocol titration schedule, changes in background medication, liver events, or use of prohibited medication or other protocol deviations. The treatment policy strategy will also be used to handle the intercurrent events for continuous endpoints.

Participants will be analyzed according to their randomized IP assignment and dose, irrespective of the treatment they actually received. Analyses will be performed using the FAS and/or per protocol analysis sets, as appropriate (Table 14). The FAS will include all randomized and treated participants who received at least one dose of IP irrespective of their protocol adherence, addition or modification of background medications, discontinuation of study intervention or switches to alternative medications, and continued participation in the study.

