## 4.2.3.4 Primary Analysis of Other Endpoints

Unless otherwise indicated, analyses of tertiary/exploratory histological endpoints and continuous exploratory endpoints at Week 48 will include both on- and off-treatment measurements while analyses of endpoints at multiple timepoints through Week 48 will only include on-treatment measurements. The treatment effect for binary exploratory endpoints will be analyzed by the Cochran-Mantel-Haenszel (CMH) test, stratified for T2DM presence and F2/F3 fibrosis stages. The difference in proportion (unstratified response difference) with Miettinen-Nurminen (ie, score-based; without stratification) 95% confidence interval, and nominal p-value from CMH chi-square test will be provided.

Continuous endpoints summarized for a single post-baseline timepoint (Week 48) will be analyzed using ANCOVA with baseline, baseline T2DM status, baseline fibrosis stage, and treatment as independent variables, using multiple imputation. If an issue is encountered for fitting an ANCOVA model (eg, collinearity with intercept), a simplified model may be used. For analysis of (absolute) change from baseline, endpoints will be analyzed without transformation and LSMEAN change from baseline by treatment; the treatment effect as the LSMD will be reported as point estimates and 95% confidence intervals with p-values provided for treatment effect. For analysis of percent change from baseline, ANCOVA will be performed using log-transformed values. Point estimates and 95% confidence intervals of percent change from baseline by treatment and ratio change from baseline will be reported with a nominal p-value for treatment effect (Section 4.2.3.2). Rubin's rules (Rubin 1987) will be used to pool LSMEAN and LSMD values and associated standard errors across multiply imputed datasets and will provide the reported estimates and p-values. The following variables will be log-transformed: ALT, AST, APRI, triglycerides, PRO-C3, FIB-4, FPG, (total and high molecular weight) adiponectin, and C-peptide. Other variables may be log-transformed if required.

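### Protocol Section 7.1 makes the laboratory inputs to six Week 48 biomarker scores optional for early discontinuers, while Section 8.5.1, the schedule of activities and the treatment-policy analysis call for those scores

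*Protocol*

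**What the plan says.** **Score inputs.** Protocol Section 8.1.5, Table 12 lists "FIB-4 index (components): platelet count, ALT, AST", "APRI (components): AST, platelet count", "NFS (components): ALT, AST, platelet count, albumin" and "BARD score (components): ALT, AST". FAST adds AST to the FibroScan measures. Agile 3+ adds AST, ALT and platelets to LSM, age, sex and diabetes status. All four analytes are in the Section 8.2.5 safety panel (Table 13), and Table 12 itself points there for ALT and AST.

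**Waiver.** Section 7.1 encourages participants who stop drug early to complete the remaining visits and procedures. It then adds that "clinical safety laboratory assessments, amylase and lipase, coagulation parameters, and calcitonin do not need to be collected at visits occurring more than 30 days", counted from the stop of study drug, apart from follow-up of laboratory abnormalities or AEs. It makes no exception for Week 48 efficacy inputs.

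**Duty to collect.** Section 8.5.1 requires the Section 8.1.5 biomarker samples from all participants, following the schedule of activities. Protocol Table 4 has rows for FIB-4 and for FibroScan with FAST and Agile 3+, both marked at Day 1, Week 48 and the early discontinuation (E/D) visit. Section 7.1 waives neither row. APRI, NFS and BARD have no row of their own.

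**Analysis.** Protocol Section 9.4.1 says that the "treatment policy strategy will also be used to handle the intercurrent events for continuous endpoints". SAP Section 4.2.3.4 says that "analyses of tertiary/exploratory histological endpoints and continuous exploratory endpoints at Week 48 will include both on- and off-treatment measurements".

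**The concern.** A computed score needs blood results. A site that follows Section 7.1 literally can skip the safety panel at Visit 11 in a participant who stopped drug months before, and still be asked by the schedule for a FIB-4, FAST or Agile 3+ score at that visit. The values made optional are the ones a treatment-policy analysis needs: SAP Section 3.3.1.2 counts liver tests and disease-specific biomarkers as on-treatment up to 30 days after discontinuation, so results beyond that point are the off-treatment ones.

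At stake is whether the Week 48 estimate for these scores describes participants as they are at Week 48, including those off drug. Comparability also suffers: ELF and Pro-C3 are outside the waiver and would be drawn at Visit 11 in the same participants.

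**Working it through.** The plan states no figure on this point to reproduce. The check counts the scores, dates the waiver, follows a skipped sample through the SAP, and tests whether a direction of bias can be claimed.

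**1. Scores affected.** Table 12 names eight disease-specific biomarkers: Pro-C3, ELF, FIB-4, APRI, NFS, BARD, FAST and Agile 3+. All but Pro-C3 and ELF use at least one safety-panel analyte, so six of eight are affected. ALT and AST as endpoints in their own right are assessed through Week 48, and the SAP analyses such endpoints on treatment only, so the waiver hardly touches them.

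**2. Participants affected.** The waiver applies at Visit 11 if the Visit 11 day minus the discontinuation day exceeds 30.
- Nominal Visit 11, Day 337: 337 − 31 = Day 306 or earlier.
- Window of ±5 days: 332 − 31 = Day 301, and 342 − 31 = Day 311.

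The documents give no discontinuation rate. Assuming 10% to 30% of about 55 randomized, 5.5 to 16.5 participants stop early across all arms. Only those who stop by about Day 306 and still attend Week 48 are exposed.

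**3. What the SAP does if the panel is skipped.** Take a participant who stops at Week 16 (Day 113). At Visit 11 the gap is 337 − 113 = 224 days, so the panel is optional.
- *FIB-4, BARD, FAST, Agile 3+.* SAP Table 6 assigns any value from Day 2 to Day 378 to Week 48, and the record closest to Day 337 is selected. The panel is drawn at the E/D visit, so an E/D score can become the Week 48 result.
- *FAST, Agile 3+.* LSM and CAP are not waived. SAP Section 4.2.3.2 computes FAST from database values with no same-visit rule, and its age rule refers to the latest collection date among a score's components. A Visit 11 LSM could be paired with an AST from the E/D visit.
- *APRI, NFS.* No SAP window table names them. If the clinical-laboratory window (SAP Table 4, Day 281 to 351) were used, E/D results before Day 281 would fall outside it and leave a gap.
- *Remaining gaps.* SAP Section 4.2.3.3 imputes single-timepoint continuous endpoints within randomized arm from fibrosis stage, T2DM status and baseline, with no term for being on or off drug. BARD is a 0 to 4 score; if handled as ordinal, it is not imputed.

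**4. Direction and size.** Set the on-drug effect to 1. Let f be the fraction of an arm that stopped but stayed, r the effect they retain off drug at Week 48, and s the effect carried by the value used in its place.
- Treatment-policy effect: 1 − f + fr
- Reported effect: 1 − f + fs
- Relative error: f(s − r)/(1 − f + fr)

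All inputs below are assumptions. A dose arm is about 55 × 2/6 = 18, so f of 0.15 to 0.25 is 2.7 to 4.5 participants.

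| f | r | s | Relative error |
|---|---|---|---|
| 0.15 | 0.5 | 1 | 0.075/0.925 = +8% |
| 0.15 | 0 | 1 | 0.15/0.85 = +18% |
| 0.25 | 0.5 | 1 | 0.125/0.875 = +14% |
| 0.25 | 0 | 1 | 0.25/0.75 = +33% |
| 0.25 | 0.5 | 0.5 | 0 |
| 0.25 | 0.5 | 0 | −0.125/0.875 = −14% |

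The sign is that of s − r, and the documents fix neither.

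**The case against.** The strongest reply is that the protocol already secures these samples. Section 8.5.1 makes the Section 8.1.5 samples mandatory for everyone, early discontinuers stay on the schedule, and the schedule keeps FIB-4, FAST and Agile 3+ at Week 48. On that reading Section 7.1 lifts a safety duty and leaves the biomarker duty in place. The Laboratory Manual, which also governs Table 12 and is not available here, might specify a separate draw. This reading is tenable, but Section 7.1 does not state it, and APRI, NFS and BARD have no schedule row to rely on. The conflict therefore stands.

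A reader might infer that the Week 48 scores cannot be computed for early discontinuers. The documents do not go that far: the waiver is permission and not a prohibition, it starts only after 30 days, and it excepts abnormalities and AEs.

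A reader might also infer that the treatment effect is overstated, by 8% to 33%. That range requires the substituted value to carry the full on-drug effect (s = 1). Protocol Section 2.1 describes dose- and time-dependent effects in the earlier NASH study, the 600 µg target is reached only at Week 24, and participants who cannot reach 200 µg stop drug. An E/D value from such a participant reflects low dose and short exposure, and the error could be zero or negative.

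Two further limits are fair. FAST and Agile 3+ are already incomplete by design, because they depend on site equipment and software. And all these endpoints are exploratory, with nominal p-values, in a discontinued program whose primary objective is safety.

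**Conclusion.** The conflict is real and its consequence is modest. For participants who stop by about Day 306 and attend Week 48, the inputs to six of the eight disease-specific biomarkers may not be collected at that visit. For FIB-4, BARD, FAST and Agile 3+, the SAP can then present an early-discontinuation value as Week 48. FAST and Agile 3+ can combine components from different dates, and remaining gaps in the continuous scores are imputed without regard to treatment status. The Week 48 estimate may then not describe off-drug status, which the stated strategy asks it to include.

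The direction and size of any bias depend on how many stop and stay, how long and at what dose they were treated, and how much effect persists. The documents give none of these. The tabulated errors show only that either sign is possible. The conclusion assumes that no separate Week 48 draw of these analytes is specified elsewhere.

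**What to change.** Two sentences would reconcile the passages.

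- **Protocol Section 7.1:** state that the safety-laboratory waiver does not apply to the Table 12 score inputs (ALT, AST, platelet count and albumin) at Week 48, for every participant who attends, however long ago they discontinued.
- **SAP Section 4.2.3.2:** require all laboratory and FibroScan components of a composite score to come from the same visit, with FibroScan allowed its ±14-day window.

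The first secures a record near Day 337, which the closest-record rule would normally select over an E/D value. The second prevents mixed-date scores and is useful even if Week 48 visits are already complete, though alone it does not stop a complete E/D score from being labelled Week 48.

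The cost is one chemistry and one hematology tube for a few participants, at a visit where blood is already scheduled for ELF, Pro-C3, HbA1c, lipids, glucose, C-peptide, adiponectin and ADA.
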